- 3.19a Female patients who are not of child-bearing potential and fertile females of childbearing potential who agree to use adequate contraceptive measures from 2 weeks prior to the study and until 1 month after study treatment discontinuation, who are not breastfeeding, and who have a negative serum or urine pregnancy test within 3 days prior to the start of study treatment.
- 3.19b Male patients should be willing to abstain or use barrier contraception (i.e., condoms) for the duration of the study drug exposure and for 3 months after study treatment discontinuation.
- 3.19c Patients who have undergone stem cell transplantation (SCT), autologous or allogeneic, are eligible provided that they are > 60 days from stem cell infusion, have GVHD \leq grade 1 and are off immunosuppressive agents for > 28 days at time of registration.

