- 3.29 AML patients who are suitable for and willing to receive intensive chemotherapy
- 3.30
- a Any of the following because this study involves an investigational agent whose genotoxic, mutagenic and teratogenic effects on the developing fetus and newborn are unknown:
- Pregnant women
 - Nursing women
 - Men or women of childbearing potential who are unwilling to employ adequate contraception
- 3.30b Subject has had prescription or non-prescription drugs or other products known to be sensitive CYP3A4 substrates or CYP3A4 substrates with a narrow therapeutic index, or to be moderate to strong inhibitors / inducers of CYP3A4 which cannot be discontinued two weeks prior (alternatively 5 half lives if T1/2 is known) prior to Day 1 of dosing and withheld throughout the study until 2 weeks after the last dose of study drug (Appendix VI).

NOTE: Co-administration of aprepitant or fosaprepitant during this study is prohibited.

Note: Individual drugs exerting CYP interactions as listed in tables in Appendix VI may be continued on a case by case basis if felt essential for patient management, after discussions and discretion of the treating physician.

The preferred azole anti-fungal medication is Fluconazole (alternatively Posaconazole) which can be given during treatment with AZD1775 (section 9.5).

3.29c Patients may not be on an inhibitor of BCRP as outlined in Appendix VI.

NOTE: AZD1775 is an inhibitor of breast cancer resistance protein (BCRP). The use of statins including Atorvastatin which are substrates for BCRP are therefore prohibited and patients should be moved on to non-BCRP alternatives.

3.29d Not willing to avoid grapefruit, grapefruit juices, grapefruit hybrids, Seville oranges, pummelos, and exotic citrus fruits from 7 days prior to the dose of study medication and during the entire study due to potential CYP3A4 interaction with the study medication. NOTE: Orange juice is allowed.

3.29e

Mean resting corrected QTc interval using the Fridericia formula (QTcF) >450 msec/male and >470 msec/female (as calculated per institutional standards) obtained from 3 electrocardiograms (ECGs) 2-5 minutes apart at study entry, or congenital long QT syndrome

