Appendix IX: Childbearing Potential & Contraception

Female patients are considered to be of childbearing potential unless

- they are post-menopausal (defined as older than 50 years and amenorrhoeic for at least 12 months following cessation of all exogenous hormonal treatments),
- there is documentation of irreversible surgical sterilisation by hysterectomy, bilateral oophorectomy or bilateral salpingectomy (but not tubal ligation), or
- they are 50 years or younger but have been amenorrhoeic for at least 12 months following the cessation of exogenous hormonal treatments, and have serum follicle-stimulating hormone (FSH) and luteinising hormone (LH) levels in the postmenopausal range for the institution.

Female patients who are of childbearing potential must agree to use adequate contraceptive measures (as defined below) for the duration of study participation, and for 6 months after the final dose of study drug; cessation of birth control after this point should be discussed with a responsible physician. They also may not be breast feeding and must have a negative serum or urine pregnancy test within 72 hours prior to start of study treatment.

Acceptable methods of contraception include true abstinence in line with the preferred and usual lifestyle choice of the subject, tubal ligation, vasectomised partner, and methods listed below **Error! Reference source not found.** All methods of contraception (with the exception of total abstinence) should be used in combination with the use of a condom by their male sexual partner for intercourse. Periodic abstinence, the rhythm method, and the withdrawal method are not acceptable methods of birth control.

Should a woman become pregnant or suspect she is pregnant while participating in this study, she should inform her treating physician immediately.

Effective Methods of Contraception

Barrier Methods	Intrauterine Device Methods	Hormonal Methods

 • Cap plus spermicide • Sponge plus spermicide • Diaphragm plus spermicide 	
 • Copper T • Levonorgestrel-releasing intrauterine system (eg, Mirena®)^a 	
Any registered and marketed contraceptive agent that contains an estrogen and/or a progestational agent (including oral, subcutaneous, intrauterine, or intramuscular agents) such as
 
 • Implants • Hormone shot or injection • Combined pill • Minipill • Patch

^a This is also considered a hormonal method.

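### Contraception for women after treatment lasts 1 month under criterion 3.19a and 6 months under Appendix IX, and nothing says which governs

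*Combined protocol and SAP*

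**What the plan says.** Three places in the protocol set out what women must do.

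- **Section 3.1, criterion 3.19a** admits fertile women "who agree to use adequate contraceptive measures from 2 weeks prior to the study" and "until 1 month after study treatment discontinuation", provided that they are not breastfeeding and have a recent negative pregnancy test.
- **Appendix IX** states: "Female patients who are of childbearing potential must agree to use adequate contraceptive measures", and gives the period as "for the duration of study participation, and for 6 months after the final dose of study drug". It attaches the same two conditions, on breastfeeding and pregnancy testing.
- **Section 3.2, criterion 3.30a** excludes "Men or women of childbearing potential who are unwilling to employ adequate contraception". It gives no duration.

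A further figure, in criterion 3.19b, applies to men only: barrier contraception or abstinence "for the duration of the study drug exposure and for 3 months after study treatment discontinuation".

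**The concern.** Two passages in force give different end dates for the same obligation on the same women. A site working from Section 3 would tell a patient that she may stop 1 month after treatment. A site working from Appendix IX would tell her 6 months.

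The protocol itself shows why the difference matters. Section 1.33 reports that AZD1775 was positive in the in vitro chromosomal aberration assays and in the in vivo micronucleus assay. Criterion 3.30a gives unknown genotoxic, mutagenic and teratogenic effects as its reason for excluding pregnancy.

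The disputed months are also lightly observed. Tables 4.1 to 4.3 place pregnancy tests before registration and on day 1 of cycles, with none marked at the end-of-study visit, 30 days after the last dose. Section 10.1 ends routine adverse event reporting at 30 days. Notice of a congenital anomaly in a later-conceived child depends on the investigator happening to learn of it. After the first month, the instruction given to the patient is therefore the main safeguard, and that instruction is what the protocol states in two ways.

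**Working it through.** The plan has no calculated figure to reproduce. The check is a comparison of texts.

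| | Criterion 3.19a | Appendix IX |
|---|---|---|
| Who | Women of childbearing potential | Women of childbearing potential |
| Start | 2 weeks before the study | Study participation; no pre-study period |
| End | 1 month after treatment discontinuation | 6 months after final dose of study drug |
| Pregnancy test before treatment | Serum or urine, within 3 days | Serum or urine, within 72 hours |
| Breastfeeding | Not allowed | Not allowed |

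**Is it the same rule?** Yes. The population, the breastfeeding condition and the test window agree (3 days = 72 hours). The end of the contraception period does not, and the start differs as well.

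**Size of the conflict.** Ratio: 6 / 1 = 6. Difference: 6 − 1 = 5 months, if both clocks start on the same day.

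**Could the different starting events explain it?** The criterion counts from the end of study treatment and the appendix from the last dose of study drug. Section 7.7b uses the term study drug for AZD1775 and calls AraC standard of care, although usage elsewhere is not uniform. Section 8.2 and the notes to Table 8.32 let AraC continue while AZD1775 is held. Assume that study drug means AZD1775 alone, and let D be the months of AraC given after the last AZD1775 dose. Counting from that last dose, the criterion ends at D + 1 and the appendix at 6, so the gap is 6 − (D + 1) = 5 − D months:

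- D = 0: 5 months
- D = 1: 4 months
- D = 2: 3 months

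The gap closes only at D = 5. In Arm C and the myelofibrosis cohort there is no AraC, so D = 0. The wording of the starting events changes the gap for some women in the combination arms but does not account for it.

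**Does another passage decide?** No. Criterion 3.30a has no duration, 3.19b concerns men, 3.19a does not point to Appendix IX, and no order of precedence is given.

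**Does it reach enrolment?** Yes. Sections 6.21 and 6.23 require a signed eligibility checklist and documents showing that each criterion is met. A woman who agrees to 1 month satisfies 3.19a but has not given the agreement in Appendix IX. Section 13.5 treats as ineligible anyone who failed any eligibility criterion at registration, so sites need to know which agreement counts.

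**Who is affected?** Section 3.12 opens relapsed or refractory AML and MDS after hypomethylating-agent failure from age 18. The general age limit in 3.11 is also 18, and it applies to myelofibrosis. Newly diagnosed AML (Arm A) is limited to patients over 60.

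**The case against.** The two rules can both be obeyed: a woman who continues for 6 months also meets the post-treatment part of 3.19a. Criterion 3.15 separately requires that patients can adhere to other protocol requirements, which reaches the appendix. On this reading the appendix merely adds to the criterion.

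The practical reach may also be small. Arm A should contribute almost no one, since Appendix IX treats women over 50 with at least 12 months of amenorrhoea as not of childbearing potential, and the myelofibrosis cohort has only 7 patients. The consent form is not among the documents reviewed, so what patients are actually told is unknown. Nothing in the primary endpoint or the analysis depends on the point.

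Most of this stands as a limit on reach. It is fair that 5 months is a nominal gap and not a figure for every woman, that early stopping of contraception is a possible consequence and not a demonstrated one, and that no error in the consent form can be inferred. It does not remove the contradiction. That both rules can be met does not help a site or patient who sees only the shorter one, and 3.19a gives no sign that a longer one exists. Nor do the documents say that the appendix overrides the criterion.

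**Conclusion.** The point holds. For women of childbearing potential the protocol states two post-treatment contraception periods, 1 month and 6 months, with no means of choosing between them. The nominal difference is 5 months. It is shorter for a woman who continues AraC after her last AZD1775 dose, if study drug is read as AZD1775 alone. The conclusion rests on the two texts as they stand and needs no outside source. The number of women affected cannot be worked out from the documents.

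This is an internal inconsistency bearing on participant safety and on how eligibility is documented. It should be corrected. It has no effect on sample size, error rates or the planned analyses.

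**What to change.** Reconcile criterion 3.19a and Appendix IX to one duration. In the same edit:

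- name the event from which the period is counted, and say whether that means AZD1775 or the last of either drug;
- align the start of the period, which only 3.19a places before the study;
- state the rule in one place and have the other refer to it;
- check the eligibility checklist and the consent form against the result.

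Which duration is right is for the sponsor and the drug supplier to decide.

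The text change is a line or two. Section 18.2 requires IRB approval of the amendment and, if the consent form changes, a decision on whether patients already consented must be re-consented. No statistical section needs revision.

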3.2 Exclusion Criteria

- 3.21 Uncontrolled intercurrent illness including, but not limited to, active uncontrolled infection, known positive for active infectious hepatitis, type A, B or C (past infection allowed), or psychiatric illness/social situations that would limit compliance with study requirements.

Note: ongoing infection controlled on antibiotics/antifungal/antiviral medications are allowed.

- 3.22 Any of the following prior therapies:
 - Cytotoxic Chemotherapy ≤ 14 days prior to registration
 - Immunotherapy ≤ 14 days prior to registration
 - Biologic therapy (i.e. antibody therapies) ≤ 14 days prior to registration
 - Radiation therapy ≤ 14 days prior to registration
 - Targeted therapies (i.e. kinase inhibitors, ≤ 7 days or 5 half-life's whichever is longer)
 - For steroids or other non-cytotoxics (exception, HU) given for blast count control, patient must be off for > 24 hrs before starting therapy. NOTE: Hydroxyurea (HU) is allowed for blast count control throughout study
 - Receiving any other investigational agent which would be considered as a treatment for the primary neoplasm ≤ 28 days prior to registration
 - Patients with persistent toxicities of \geq Grade 1 from prior AML treatment (including chemotherapy, kinase inhibitors, immunotherapy, experimental agents, radiation, or surgery).

- 3.23 Active uncontrolled CNS leukemia. NOTE: Positive (cyto)pathology is allowed and patient can receive intrathecal chemotherapy
- 3.24 Immunocompromised patients and patients known to be HIV positive and currently receiving antiretroviral therapy. NOTE: Patients known to be HIV positive, but without clinical evidence of an immunocompromised state, are eligible for this trial.
- 3.25 Any previous treatment with AZD1775 or allergic reactions to excipients of AZD1775.
- 3.26 Acute Promyelocytic Leukemia (APL, M3) unless failed treatment with all available therapies known to be active for treatment of APL.
- 3.27 Major surgery \leq 28 days prior to registration
- 3.28 Clinically significant heart disease, including the following:
- Active severe angina pectoris within 3 months prior to registration
 - Acute myocardial infarction within 3 months prior to registration
 - New York Heart Association classification IV cardiovascular disease or symptomatic class III disease (Appendix III).
- Note: patients with any of the above may be allowed after discussion amongst the investigators including the principal investigator
- 3.29 AML patients who are suitable for and willing to receive intensive chemotherapy
- 3.30
- a Any of the following because this study involves an investigational agent whose genotoxic, mutagenic and teratogenic effects on the developing fetus and newborn are unknown:
- Pregnant women
 - Nursing women
 - Men or women of childbearing potential who are unwilling to employ adequate contraception
- 3.30b Subject has had prescription or non-prescription drugs or other products known to be sensitive CYP3A4 substrates or CYP3A4 substrates with a narrow therapeutic index, or to be moderate to strong inhibitors / inducers of CYP3A4 which cannot be discontinued two weeks prior (alternatively 5 half lives if T1/2 is known) prior to Day 1 of dosing and withheld throughout the study until 2 weeks after the last dose of study drug (Appendix VI).

NOTE: Co-administration of aprepitant or fosaprepitant during this study is prohibited.

Note: Individual drugs exerting CYP interactions as listed in tables in Appendix VI may be continued on a case by case basis if felt essential for patient management, after discussions and discretion of the treating physician.

The preferred azole anti-fungal medication is Fluconazole (alternatively Posaconazole) which can be given during treatment with AZD1775 (section 9.5).

3.29c Patients may not be on an inhibitor of BCRP as outlined in Appendix VI.

NOTE: AZD1775 is an inhibitor of breast cancer resistance protein (BCRP). The use of statins including Atorvastatin which are substrates for BCRP are therefore prohibited and patients should be moved on to non-BCRP alternatives.

3.29d Not willing to avoid grapefruit, grapefruit juices, grapefruit hybrids, Seville oranges, pummelos, and exotic citrus fruits from 7 days prior to the dose of study medication and during the entire study due to potential CYP3A4 interaction with the study medication. NOTE: Orange juice is allowed.

3.29e

Mean resting corrected QTc interval using the Fridericia formula (QTcF) >450 msec/male and >470 msec/female (as calculated per institutional standards) obtained from 3 electrocardiograms (ECGs) 2-5 minutes apart at study entry, or congenital long QT syndrome

3.30 Herbal preparations/medications are generally not allowed throughout the study. These herbal medications include, but are not limited to: St. John's wort, kava, ephedra (ma huang), ginkgo biloba, dehydroepiandrosterone (DHEA), yohimbe, saw palmetto, and ginseng. Patients should stop using these herbal medications 7-14 days prior to first dose of AZD1775. If there is no known potential interaction between an herbal medication and AZD1775, the protocol principal investigator can give a waiver to continue such medication, with the expectation of St. John's wort, kava, ephedra (ma huang), ginkgo biloba, dehydroepiandrosterone (DHEA), yohimbe, saw palmetto, and ginseng, that are not allowed at any stage.

4.0 Test Schedule

Table 4.1: Test Schedule for Elderly Newly Diagnosed and Relapsed/Refractory AML patients

Tests and procedures	Active Monitoring Phase					
	≤14 days prior to registration	≤7 days prior to registration	Cycle 1 Days 1, 4, 8, 15, & 28(±3 days) ^{5, 16}	Cycles 2 & 3 Days 1, 15, and 28 (± 3 days) ^{5, 16}	Cycles 4+ and Beyond Day 1 (±3 days) ^{5, 16}	EOS ₂
History and exam, wt, PS, vitals	X		X	X	X	X
Height	X					
Adverse event assessment	X		X	X	X	X
Hematology group WBC ANC Hgb PLT		X	X _A	X _B	X ₉	X
Chemistry group: sodium, potassium, calcium, creatinine, bicarbonate, glucose, chloride, albumin, BUN, alkaline phosphatase, AST, ALT, total protein, total bilirubin, LDH		X	X _A	X _B	X	X
TLS monitoring (for selected AML patients): BUN, calcium, CO ₂ , chloride, creatinine, glucose, potassium, sodium, uric acid, phosphorus			X ₁₃			
PT/PTT and D-dimer			X ₁₈			
Serum pregnancy test ₁		X		X	X	
Bone marrow biopsy and aspirate procedure (cytogenetics or FISH) ¹⁴	X ₁₁		X ₃	X ₃	X ₃	X ₁₀
Bone marrow aspirate research specimens (see Section 14.0) _R	X ₈		X ₇	X ₇	X ₇	X ₆
Blood specimens (see Section 14.0) _R	X _{4, 8}		X ₄	X ₄	X ₄	X ₄

Saliva Sample, see Section 14.0) ^R	X					
Patient Questionnaire Booklet ¹²	X		X ₁₅	X ₁₅	X ₁₅	X ₁₅
ECG (12 lead) ¹⁷		X	X _C	X	X	X

1. For women of childbearing potential only. Day 1 of each cycle
2. 30 days (+/-3days) post last dose of study drug
3. For AML patients: marrow aspirates and biopsies will be done after cycle 1 (at physician's discretion), after cycles 2 and 4, and then at physician discretion). In addition, bone marrow should be performed at time of suspected CR/CRi and/or disease progression and at physician discretion as clinically indicated. Note: Bone Marrow Aspirate and biopsy may be avoided after cycle 4 as determined by study chair or treating physician (i.e. if determined to not yield information that would change clinical management).
4. Blood specimens for research sampling to be collected as defined in Section 14.
5. Day 1 assessments do not need to be repeated if pre-registration or Day 28 assessments completed within 72 hours of Day 1.
6. Only if an EOS marrow sample is collected as part of standard of care
7. Research bone marrow samples are to be collected at the same time when a marrow is done as part of patient's standard of care, including research marrow samples should be drawn at time of marrow for suspected CR/CRi and/or disease progression.
8. To be collected on all patients at baseline. If no baseline marrow samples obtained, the peripheral blood research sample becomes mandatory to participate in study. Bone marrow aspirate specimens must be collected and submitted per section 14.0. If bone marrow performed at end of study as part of patient's standard of care, collect sample per section 14.0.
9. After 2 cycles, CBC frequency may be reduced at treating physician's discretion but needs to be performed at least once per cycle.
10. Progression marrow can be used as EOS marrow if patient is taken off trial based on the results. Additional EOS bone marrow can be omitted if a progression marrow was done, or an EOS marrow can be done at physician discretion and is optional.
11. ≤ 28 days prior to registration; for patients with an outside marrow biopsy within 4 weeks of study start, outside results can serve as baseline after review at NYU.
12. Patient questionnaire booklet must be used; copies are not acceptable for this submission. Booklet should be completed by patient prior to review of treatment response and discussions of patient's general health since last treatment evaluation.
13. For patients at high risk of tumor lysis syndrome (TLSTLS labs will be performed at least twice during the first week of therapy, when maximum TLS risk is highest. . Additional monitoring will be done on a case by case basis.
14. Either conventional cytogenetics or FISH panel (or both based on physician discretion) for AML to be performed at baseline. If diploid cytogenetics at baseline, subsequent cytogenetic studies may be omitted unless disease progression is suspected. For FISH based cytogenetic assessments, an entire AML FISH panel should be performed at baseline, while on subsequent marrows only positive specific FISH abnormalities/probes need to be repeated unless disease progression is suspected, in which case a full AML FISH panel or instead conventional cytogenetics should be performed.
15. Booklets to be completed at end of all cycles.
16. Prior to the start of treatment.
17. ECG in triplicate on day1 of each cycle, for cycle 1, ECGs will be conducted at least weekly.
18. To be tested on C1D1 prior to treatment.
 - A. For AML patients, CBC and blood chemistries will be collected at least twice weekly for Cycle 1
 - B. For AML patients, CBC and blood chemistries will be collected weekly for Cycle 2
 - C. For cycle 1, ECGs will be conducted at least weekly.
 - R. Research funded (see Section 19.0).

Table 4.2: Test Schedule for HMA failure MDS/ AML patients

Tests and procedures	Active Monitoring Phase					
	≤14 days prior to registration	≤7 days prior to registration	Cycle 1 Days 1, 8, 15, & 28(± 3 days) ^{12, 10}	Cycle 2 Days 1, 15, and 28 (± 3 days) ^{10, 12}	Cycles 3+ and Beyond Day 1 (±3 days) ^{10, 12}	EOS ₂
History and exam, wt, PS, vitals	X		X	X	X	X
Height	X					
Adverse event assessment	X		X	X	X	X
Hematology group WBC ANC Hgb PLT		X	X	X	X	X
Chemistry group: sodium, potassium, calcium, creatinine, bicarbonate, glucose, chloride, albumin, BUN, alkaline phosphatase, AST, ALT, total protein, total bilirubin, LDH		X	X _A	X _B	X	X
Serum Erythropoietin level	X					
Serum pregnancy test ¹		X		X	X	
Bone marrow biopsy and aspirate procedure (cytogenetics or FISH ⁹)	X ₆			X ₃	X ₃	X ₇
Blood specimens (see Section 14.0) _R	X _{4,13}		X ₄	X ₄	X ₄	X ₄
Saliva Sample (see Section 14.0) _R	X					
Bone marrow aspirate research specimens (see Section 14.0) _R	X _{6, 13}			X ₅	X ₅	X ₅
Patient Questionnaire Booklets ⁸	X				X ₈	X
ECG (12 lead) ¹¹		X	X _C	X	X	X

1. For women of childbearing potential only Day 1 of each cycle
2. 30 days (+/-3days) post last dose of study drug
3. Marrow biopsies only to be done at End of cycle 2, End of cycle 4, at time of suspected CR/CRi and thereafter at physician discretion as clinically indicated (i.e. disease progression).

4. Blood specimens for research sampling to be collected as defined in Section 14.
5. Research marrow samples (aspirates) to be done at times of clinical standard of care marrow tests at End of cycle 2, End of cycle 4, at time of suspected CR/CRi or disease progression and thereafter at physician discretion as clinically indicated. A sample will be obtained at end of study (EOS) if a bone marrow is performed as part of patient's standard of care; sample will be collected per section 14.0
6. ≤ 28 days prior to registration; for patients with an outside marrow biopsy within 4 weeks of study start, outside results can serve as baseline after review at NYU.
7. Bone marrow at end of study is only to be done at physician discretion and is optional. Progression marrow can be used as EOS marrow if patient is taken off trial based on the results.
8. Patient questionnaire booklet must be used; copies are not acceptable for this submission. Booklet should be completed by patient prior to review of treatment response and discussions of patient's general health since last treatment evaluation. Booklets to be completed at baseline, cycles 3, 6, 9, and EOS.
9. Either conventional cytogenetics or FISH panel (or both based on physician discretion) for MDS should be performed at baseline. If diploid cytogenetics at baseline subsequent cytogenetic studies may be omitted unless disease progression is suspected. For FISH based cytogenetic assessments, an entire MDS FISH panel should be performed at baseline, while on subsequent marrows only positive specific FISH abnormalities/probes need to be repeated unless disease progression is suspected.
10. Prior to the start of treatment.
11. ECG in triplicate on day1 of each cycle,
12. Day 1 assessments do not need to be repeated if pre-registration or Day 28 assessments completed within 72 hours of Day 1.
13. To be collected on all patients at baseline. If no baseline marrow samples obtained, the peripheral blood research sample becomes mandatory to participate in study. If collected bone marrow aspirate specimens must be collected and submitted per section 14.0. If bone marrow performed at end of study as part of patient's standard of care, collect bone marrow sample per section 14.0.
 - A For AML patients, CBC and blood chemistries will be collected at least twice weekly for Cycle 1. TLS labs will be performed at least twice during the first week of therapy
 - B For AML patients, CBC and blood chemistries will be collected weekly for Cycle 2
 - C For cycle 1, ECGs will be conducted at least weekly.
 - R Research funded (see Section 19.0).

Table 4.3: Test Schedule for MF patients

Tests and procedures	Active Monitoring Phase					
	≤14 days prior to registration	≤7 days prior to registration	Cycle 1 Days 1, 15, & 28(± 3 days) ^{12, 10}	Cycle 2 Days 1, 15, and 28 (± 3 days) ^{10, 12}	Cycles 3+ and Beyond Day 1 (±3 days) ^{10, 12}	EOS ²
History and exam, wt, PS, vitals	X		X	X	X	X
Height	X					
Adverse event assessment	X		X	X	X	X
Hematology group WBC ANC Hgb PLT		X	X	X	X	X
Chemistry group: sodium, potassium, calcium, creatinine, bicarbonate, glucose, chloride, albumin, BUN, alkaline phosphatase, AST, ALT, total protein, total bilirubin, LDH		X	X	X	X	X
Serum Erythropoietin level	X					
Serum pregnancy test ¹		X		X	X	
Bone marrow biopsy and aspirate procedure (cytogenetics or FISH ⁹)	X ⁶			X ³	X ³	X ⁷
Blood specimens (see Section 14.0) ^R	X ^{4,13}		X ⁴	X ⁴	X ⁴	X ⁴
Saliva Sample (see Section 14.0) ^R	X					
Bone marrow aspirate research specimens (see Section 14.0) ^R	X ^{6, 13}			X ⁵	X ⁵	X ⁵
Patient Questionnaire Booklets ⁸	X		X ⁸	X ⁸	X ⁸	X
ECG (12 lead) ¹¹		X	X	X	X	X

1. For women of childbearing potential only Day 1 of each cycle
2. 30 days (+/-3days) post last dose of study drug
3. Marrow biopsies only to be done at End of cycle 2, End of cycle 4, at time of suspected CR/CRi and thereafter at physician discretion as clinically indicated (i.e. disease progression).

4. Blood specimens for research sampling to be collected as defined in Section 14.
 5. Research marrow samples (aspirates) to be done at times of clinical standard of care marrow tests at End of cycle 2, End of cycle 4, at time of suspected CR/CRi or disease progression and thereafter at physician discretion as clinically indicated. A sample will be obtained at end of study (EOS) if a bone marrow is performed as part of patient's standard of care; sample will be collected per section 14.0
 6. ≤ 28 days prior to registration; for patients with an outside marrow biopsy within 8 weeks of study start, outside results can serve as baseline after review at NYU.
 7. Bone marrow at end of study is only to be done at physician discretion and is optional. Progression marrow can be used as EOS marrow if patient is taken off trial based on the results.
 8. Patient questionnaire booklet must be used; copies are not acceptable for this submission. Booklet should be completed by patient prior to review of treatment response and discussions of patient's general health since last treatment evaluation. Booklets to be completed at end of all cycles.
 9. Either conventional cytogenetics or FISH panel (or both based on physician discretion) for MDS should be performed at baseline. If diploid cytogenetics at baseline subsequent cytogenetic studies may be omitted unless disease progression is suspected. For FISH based cytogenetic assessments, an entire MDS FISH panel should be performed at baseline, while on subsequent marrows only positive specific FISH abnormalities/probes need to be repeated unless disease progression is suspected.
 10. Prior to the start of treatment.
 11. ECG in triplicate on day1 of each cycle. NOTE: for cycle 1, ECGs will be conducted at least weekly.
 12. Day 1 assessments do not need to be repeated if pre-registration or Day 28 assessments completed within 72 hours of Day 1.
 13. To be collected on all patients at baseline. If no baseline marrow samples obtained, the peripheral blood research sample becomes mandatory to participate in study. If bone marrow aspirate specimens obtained must be collected and submitted per section 14.0. If bone marrow performed at end of study as part of patient's standard of care, collect peripheral blood sample instead per section 14.0.
- R Research funded (see Section 19.0).

5.0 Grouping Factors:

